To identify adverse events: (1) study staff will perform a clinical review at each study visit and (2) study staff will instruct participants to report any unexpected or severe adverse events to their assigned research assistant. Such a report will immediately be brought to the attention of study principal investigators. Any adverse events that are unanticipated (i.e., not related to standard HTN clinical care or thought to be directly related to study procedures) or severe (e.g. death) will be recorded on an adverse events log form and brought to the attention of the principal Investigator, as well as be reported to participating ethical review committees within 7 days. The relevant committee will determine whether it is appropriate to pause the study or alter the study protocol and will provide suggestions/modifications to the study procedures as necessary. Possible modifications include adding adverse events to the consent form and re-consenting all study participants. The site principal investigator will be responsible for monitoring participant safety at each site on a monthly basis at regularly scheduled research meetings. They will keep a written log of all events and ensure that the ethical review committee is contacted when necessary. They will also keep a log of the outcome of committee decisions regarding adverse events and apprise the research team of any changes that need to occur as a result of such decisions.

J. Statistical Considerations and Analyses

a. Sample Size

Based on prior studies we anticipate a mean blood pressure of 150/95 mmHg among

randomized participants with a standard deviation of 19 mmHg [5]. To detect a 5 mmHg difference between arms in the change of blood pressure from baseline to 6 months, we will need to enroll 774 participants (258 per arm) to provide 80% power, assuming 20% loss to follow-up, a correlation between baseline and follow-up measurements of 0.5, and an alpha of 2.5% to account for multiple testing with comparison between the SOC and both intervention arms (Table 2). This same sample size will also give us greater than 80% power to detect an increase in the proportion of participants who achieve BP control (defined by a systolic BP <140 mmHg and diastolic BP <90mm Hg) at 6 months from 30% in the SOC arm to 45% in the interventions arms, or from 40% in the SOC to 56% in the intervention, also allowing for an alpha of 2.5% to account for multiple testing. We estimate that there are over 2,500 individuals to draw this sample from within our catchment area served by the three most heavily population primary care clinics in the catchment area (Table 3).

Table 2. Differences in change from baseline that can be detected with 80% power

330	264	5.0	19.0	0.20	80%
258	206	5.0	19.0	0.50	80%
148	118	7.5	19.0	0.20	80%
115	92	7.5	19.0	0.50	80%

Table 3. Hypertension visits and patients at clinics in the study catchment area (2020)

Clinic	Hypertension Visits	Patients with Hypertension	Patients with Uncontrolled Hypertension
Esiyembeni	458	152	163
Gunjaneni	1481	424	245
Hluhluwe	1010	406	828
KwaMsane	1997	768	168
Machibini	1692	428	7
Madwaleni	814	406	507
Mpukunyoni	1277	569	63
Mtubatuba	1089	545	36
Nkundusi	1392	465	578
Ntondweni	869	288	163
Somkhele	1685	652	245
Totals	13764	5103	2595

K. Study Outcomes

- a. Primary Outcome of Clinical Trial: Difference between arms in change from baseline in systolic blood pressure (SBP) 6 months after enrollment.
- b. Secondary Outcomes:
 - Proportion with blood pressure control at 6 after enrollment (<140/90 mmHg).
- c. Safety Measures:
 - Number of adverse drug reactions.
 - Proportion of participations retained in hypertension care at 6 months.

L. Aim 2 Analysis Plan

We will summarize participant sociodemographic and clinical characteristics at baseline in all three arms. We will use linear regression to estimate the difference between arms, and its 95% confidence interval (CI), in systolic blood pressure at 6 months, adjusted for baseline systolic BP. We will use logistic regression to estimate odds ratios (OR) and 95% CIs for the impact of the intervention on the proportion of participants who achieve blood pressure control (<140/90) at 6 months.

Characteristics of individuals who are lost to follow-up will be tabulated by study arm. Since study nurses will visit all participants at home to measure blood pressure at 6 and 12 months, we do not expect there to be differential loss to follow-up between arms. In the primary analyses, participants with missing data at 6 months will be excluded. In sensitivity analyses, those with missing measurements will be considered to have no change in systolic BP and uncontrolled BP. Missing values may also be imputed using multiple imputation.

In pre-planned secondary analyses, we will fit regression models stratified by sex (to assess for sex as a biologic variable), age strata, socioeconomic status and baseline co-morbidities (i.e. obesity and HIV) to determine sub-group effect sizes and test the significance of an interaction term between sub-groups and the intervention to assess for effect modification.

A detailed statistical analysis plan will be prepared before the data are examined by treatment arm.

M. Risks, Protection from Risks and Benefits to Study Participation in Aim 2

a. Risks and Protections

One risk to participation is breach of confidentiality. Study staff will be trained in confidentiality and all staff members will be required to sign confidentiality agreements. Assurance of privacy in testing and communication of results will be done. Quality assurance processes will include regular support/supervision visits in the field and self-evaluations in this study. To ensure confidentiality of participants, all data will be coded by subject number. Data recorded on paper will be kept in locked cabinets with access only by members of the research team. There will be strict limited access to electronically stored data as well, using password protection. Research records will be kept confidential following national regulations. The subject's name or other personal identifiers will not be included with specimens sent to the laboratory, which will be identified only by a code number. Interviewers and support staff will be trained on procedures for maintaining confidentiality.

We will conduct a single specimen collection during this study to conduct point of care creatinine testing that will be administered by trained study staff. A trained nurse will collect blood from a pin prick using standard precautions requiring a few drops of blood (< 1ml) to be drawn.

Study participants in both the SOC and intervention arms with uncontrolled hypertension will receive one of four blood pressure medications on the South African Essential Medication list according to the local guidelines including: hydrochlorothiazide, enalapril or other angiotensin converting enzyme inhibitor, amlodipine, or a beta-blocker. No experimental medications will be used. Participants will be followed for side-effects in accordance with the South African hypertension guidelines by the nurses and the CBPMs. All participants who experience any adverse event will receive follow-up until adverse event is resolved by the local study staff. Severe and serious adverse events will

be documented and reported to the involved regulatory bodies per their regulations. A secondary risk of participation in this Aim is loss of time from participation in interviews and/or discomfort with the questions asked or nature of the conversations. All participation will be voluntary and participants will be free to pause, interrupt, or not respond to any questions or content areas that make them uncomfortable.

Participants in the CBPM and eCBPM+ arms of the study have a risk of receiving less than the standard of care by not attending the clinic, particularly if data from the home blood pressure cuffs are not being transmitted manually or automatically to the clinical decision support system. Protections will be in place such that the nurses who remain the backbone of hypertension care in all intervention and control clinics will have the ability to communicate with the CBPM to ensure a) blood pressure data is transmitted properly or faulty equipment is repaired or replaced, b) prescriptions are available for patients or delivered as allowed, or c) communicate through the CBPMs so that the participant can come in for a visit or make a home visit to ensure that care consistent with guidelines is available to all participants.

b. Benefits

Participants may lead to a reduction in their blood press level and overall improved blood pressure control. Participants in the intervention arm may develop proficiency in managing their own blood pressure and learning about the operation of a home blood pressure device.

Participants may gain a better understanding of their cardiovascular risk profile. Any identified with having advanced renal disease may be referred for additional care and therapy.

Some participants might gain a personal sense of pride from knowing they are contributing to development of a system that intends to improve hypertension care in their community, or for the opportunity to contribute to its design.

If one of the interventions is ultimately successful, this study might provide a benefit to the community by helping to guide development of an improvement system of hypertension care.

A financial incentive of R450 will be paid to participants for participation in the clinical trial. An incentive of R150 will be given after each study visit at baseline, month 6 and month 12. These incentives are consistent with current SAHPRA recommendations.

VI. AIM 3

Determine the fidelity, sustainability, acceptability, and cost-effectiveness of community-based, technology-supported hypertension interventions to reduce blood pressure in rural KwaZulu-Natal.

Aim 3 will have two primary components:

(3a) Building on the qualitative research conducted before and early in the trial, we will conduct additional qualitative research to assess the acceptability of the interventions and quantitative monitoring of implementation throughout the trial to assess fidelity and sustainability.

(3b) We will record the costs of care and of the interventions and determine the cost-effectiveness of the intervention with microsimulation model (CVD PREDICT) that uses individual-level risk factor data and health cost inputs.

A. Methods

a. (Aim 3a) Fidelity, Sustainability, and Acceptability

The use of the CMIR and TFA (Aim 1) will be extended to evaluate the overall acceptability, fidelity, and sustainability of the intervention.

Approximately 12 months after the start of the trial we will conduct key informants interviews and individual interviews with health workers and trial participants. Where appropriate we will include the same individuals sampled for Aim 1, to compare their experiences during the trial with their initial expectations and preferences. Qualitative data collection and analysis will be similar to Aim 1 methods, adapted as necessary to accommodate unforeseen issues that arise during the trial.

Study documentation (e.g. coordination meeting minutes, supervision visit reports) will be reviewed to extract any relevant information contributing to document adaptations to implementation, and thereby fidelity, decision-making process and thereby acceptability (and feasibility), and short-term sustainability.

These qualitative data will be complemented by collection of quantitative indicators of fidelity and sustainability of implementation. An assessment of the intervention's fidelity will be performed 6 and 12 months after study enrollment (based on monthly data collection), while sustainability will be measured at the 12-month, 18-month, and 24-month visits. Data will be collected through repeated completion of intervention fidelity clinic checklists to estimate adherence, exposure, and quality of the intervention.

b. (Aim 3b) Cost-effectiveness

Cost-effectiveness of the intervention compared to standard of care in blood pressure management, will be calculated as incremental costs for absolute changes in blood pressure (costs/mmHg) and incremental costs per extra participant with controlled blood pressure. The Harvard CVD PREDICT microsimulation model for cost-effectiveness and changes in CVD-related health outcomes will be used to conduct this analysis. The cost-effectiveness will be calculated across the entire intervention, as well as separately by each of the study arms.

B. Study Outcomes

a. (Aim 3a) Fidelity, Sustainability, and Acceptability

Study outcomes measuring acceptability, fidelity, and sustainability of the intervention are summarized below in **Table 4**.

c. (Aim 3b) Cost-effectiveness

- Costs to participants of health care including (where applicable) the interventions
- SBP reduction and blood pressure control resulting from the interventions
- Quality adjusted life years (QALYs)
- Incremental cost-effectiveness ratios (ICERs), that is, incremental cost per mmHg SBP reduction, per extra participant with controlled blood pressure, and per QALY gained as effects of the interventions

Table 4. Summary of acceptability, fidelity, and sustainability outcome measures for Aim 3a

Acceptability	
 - Participant and provider perception of the intervention and clinical decision support tools. 	
 - Key informants interviews. - Individual interviews.
Fidelity	
 - Proportion of successful and failed BP data transmission events, among all transmitted BP data events. - Proportion of CDS-recommended treatment changes initiated by nurse/CBPM, among all CDS-recommended treatment changes. - Number of BP cuffs distributed to participants in 2 intervention arms. - Number of BP readings manually recorded by intervention participants. - Number of CBPMs trained on HBPM and data tool input/management. - Number of participants with treatment initiation during study period. - Number of BP cuff training sessions provided to participants at home by CBPMs. - Number/frequency of CBPM home visits conducted versus planned 	
 - Study check lists. - CDS records. - Study check lists. - Participant study records. - Outreach team leader supervision records. - CBPM study records. - CBPM study records
Sustainability	
 - Number of participants counseled in lifestyle modification and medication adherence at home by CBPMs. - Number of clinics adopting use and distribution of BP cuffs for HBPM. - Proportion of clinics sustaining use and distribution of BP cuffs for HBPM at 12 months, among those who distributed BP cuffs at the start of the study. - Proportion of participants retained in hypertension care at 12 months, among enrolled study participants. - Absolute change in systolic blood pressure (SBP) between 6 and 12 months after enrollment, among enrolled study participants. - Proportion of participants retained in hypertension care at 12 months, among enrolled study participants. - Absolute change in systolic blood pressure (SBP) between 6 and 12 months after enrollment, among all study participants. 	
 - CBPM study records. - Study check lists. - Study check lists. - Participant study records. - CDS records - Participant study records. - CDS records.

C. Data Sources

a. (Aim 3a) Fidelity, Sustainability, and Acceptability

Both the fidelity and the sustainability of the intervention will be assessed using data obtained through review of study check lists, the participant study records (including prescriptions), CDS records, CBPM study records, outreach team leader supervision records, and coordination meeting minutes.

Key informant and individual interviews will assess overall acceptability and experience of the intervention.

b. (Aim 3b) Cost-effectiveness

Cost data will be obtained from trial participant interviews, KZN DoH unit prices, and analysis of intervention delivery.

The trial will provide individual level outcome data on SBP and blood pressure control 6 and 12 months. The PREDICT model will use these data to predict long term effects of the interventions on quality adjusted life years (QALYs)

D. Recruitment

a. (Aim 3a) Fidelity, Sustainability, and Acceptability

As appropriate, for key informants and individual interviews, we will try to recruit from the same sample used in Aim 1 in order obtain maximal information about changes in expectations and experiences before and after the trial. Key informants will be identified and contacted by study investigators at AHRI from current and prior collaborators working on improving health care in this rural population. Health care workers will be identified from personnel records at the study clinics and be invited to participate in interviews by study investigators. Participants will be identified from clinic registers for hypertensive patients.

b. (Aim 3b) Cost-effectiveness

Participants will not be enrolled for this part of Aim 3 and cost data will be obtained as described in Section C(b) above.

E. Enrollment

a. (Aim 3a) Fidelity, Sustainability, and Acceptability

i. Inclusion Criteria for Key Informants

- age 18 and over.
- representative of the KZN DoH for involved in management of primary care delivery programs.

ii. Inclusion Criteria for Health Care Workers

- age 18 and over.
- currently employed as a health care worker (physician, nurse, CHW, pharmacist, clinic administrator/operational manager) at one of the study clinics.

iii. Inclusion Criteria for Participants

- age 18 and over.
- diagnosed with uncontrolled hypertension.
- selection based on pre-defined criteria such as age, gender, trial arm, patients accepting/refusing the intervention.

- b. (Aim 3b) Cost-effectiveness
Not applicable

F. Sample Size

- a. (Aim 3a) Fidelity, Sustainability, and Acceptability
- Key informants interviews: minimum 5
 - Interviews with professional health care workers: minimum 15 (3 per facility), including chronic nurse, OM, nurse “supervising” CHW, doctors (supervisory role)
 - Interviews with CHW (minimum 3 per clinic)
 - Interviews with patients: minimum 15
- b. (Aim 3b) Cost-effectiveness
All trial participants will be included in analysis of costs and cost effectiveness.

G. Informed Consent

- a. (Aim 3a) Fidelity, Sustainability, and Acceptability
As in Aim 1, key informant discussants will be invited to participate in discussions about the planned study and their participation in meetings will be taken as consent to participate.
Study research assistants will recruit participants enrolled in the study and health care workers to participate in the focus groups.

Persons who participated in Aim 1 activities and who will participate in Aim 3 activities, will be re-consented regardless of whether they provided verbal or written consent in Aim 1. Consenting procedures for Aim 3 will be identical to those described in Aim 1.

- b. (Aim 3b) Cost-effectiveness
This will be included in the consent to participate in the trial.

H. Data Collection

- a. (Aim 3a) Fidelity, Sustainability, and Acceptability
Data on fidelity outcomes will be obtained from study checklists and data collected with the electronic hypertension management tool in the intervention arms at 6, 12, 18 and 24 months. Sustainability measures, including changes in systolic blood pressure, will be collected using the same sources at 12 months in the intervention arms. In the standard of care arm changes in systolic blood pressure at 12 months and medication use will be obtained through participant chart reviews. All data will be combined into a database for analyses and all personal identifiers will be removed prior to analysis. Interviewers will use guides with open-ended questions to collect qualitative data on the overall acceptability of the intervention.
- b. (Aim 3b) Cost-effectiveness
Resource allocation assessments in all three study arms will be conducted at 6 and 12 months after the start of the trial using a time and motion study over five clinic days, along with medical records reviews and participant exit interviews. Using these measurements, the public-sector unit costs for managing hypertension will be calculated, including human resources, diagnostics and supplies, therapeutics, and home blood pressure monitors. Costs will be collected from relevant sources, including clinic sites, the South African

Department of Health, and published reports. A societal perspective will be applied to data collection and analysis.

I. Analysis

a. (Aim 3a) Fidelity, Sustainability, and Acceptability

Quantitative data will be analyzed using Stata Statistical Software (Release 17. College Station, TX) and statistics for fidelity and sustainability outcomes will be generated. Qualitative data analysis will be performed using similar methods as in Aim 1. The key informants and individual interviews will be collected in isiZulu, then transcribed, and translated in English by a team of social science research assistants. A data-led coding framework will be developed, based on themes, which emerge from the data. The research assistants involved in collecting the data will work with other social science team members to agree on the coding framework and performing coding of the data. Thematic summaries will be prepared using the data and a process of building consensus among the whole study team. These summaries will form the building blocks for reporting the findings. Organization of data on the acceptability of the intervention will again be organized into component constructs using the Theoretical Framework for Acceptability, as described in Aim 1.

b. (3b) Cost and Cost-effectiveness

Cost-effectiveness of the intervention compared to standard of care in blood pressure management, will be calculated as incremental costs for absolute differences in blood pressure (costs/mmHg) and incremental costs per extra participant with controlled blood pressure. This analysis will be performed using the Harvard CVD PREDICT model [15] for cost-effectiveness and changes in CVD-related health outcomes. The model will be used to assess the cost-effectiveness of the intervention and to model the impact on the observed change in systolic blood pressure on future CVD events. We will also use the model to translate the intervention effectiveness established during the trial into quality adjusted life years (QALY) and applying assumptions about effects of SBP reductions on survival, quality of life, and complications, based on the extant literature and confirmed locally as part of this trial.

The cost-effectiveness will be calculated across the entire intervention, as well as separately by each of the study arms and expressed in incremental cost-effectiveness ratios (ICERs) and quality adjusted life years (QALYs).

If there is a significant reduction in SBP, we will measure the long term expected reductions in major cardiovascular events and mortality in the population beyond the study period, and for a nationally scaled population. For these predictive cost-effectiveness analyses, we will assess the costs and cost-effectiveness of the intervention modeling the impact on the change in SBP on future CVD events.

Health-related quality of life is measured using the time trade off approach for a reference population in sub-Saharan Africa as adopted in similar cost-effectiveness analyses. We will conduct probabilistic sensitivity analysis by defining probability distributions of variables in the model used to calculate the costs and effectiveness.

We will develop the cost-utility model using best practices outlined by the ISPOR Good Research Practice Task Force [16-19] and guidelines set out by the US Second Panel on

Cost-Effectiveness in Health and Medicine.

J. Risks, Protection from Risks and Benefits to Study Participation in Aim 3a and 3b

a. Risks and Protections

- i. The primary risk to participation is breach of confidentiality. We will not record names of any individuals taking part in interviews, nor will we report them in findings to be disseminated as part of this project. Given the low number of people in the study and the identification of participants (e.g., stakeholders in the Department of Health) it is possible that their identities could be inferred and we will make this risk clear during the consenting process.
- ii. A secondary risk of participation in this aim is loss of time from participation in interviews and/or discomfort with the questions asked or nature of the conversations. All participation will be voluntary and participants will be free to pause, interrupt, or not respond to any questions or content areas that make them uncomfortable.

b. Benefits

- i. Most study participants in Aim 3 will derive no direct benefit from participation in the study.
- ii. Some participants might gain a personal sense of pride from knowing they are contributing to development of a system that intends to improve hypertension care in their community, or for the opportunity to contribute to its design.
- iii. If one of the interventions is ultimately successful, this study might provide a benefit to the community by helping to guide development of an improvement system of hypertension care.

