a. Inclusion Criteria

- Age greater than 18 years old.
- Residing in uMkhanyakude District in northern KwaZulu-Natal in an area that is served by a CBPM.
- Elevated blood pressure (blood pressure > 140/90 mmHg) on two measurements.

b. Exclusion Criteria

- Pregnant or breast-feeding women.
- Severe, symptomatic hypertension with a measured blood pressure > 180/110 mmHg.
- Known, advanced chronic kidney disease. GFR < 60 ml/min/1.73 m².
- Current use of at least 3 different anti-hypertensive therapies at full dose.
- Planning to move within the next 24 months.

D. Subject Recruitment

a. Participant Identification

We will identify potentially eligible participant from three sources: 1) those presenting to the trial clinics with elevated blood pressure, 2) individuals who are diagnosed with hypertension during home visits by CBPMs, or 3) individuals with elevated blood pressure identifying through screening activities for hypertension conducted in the study catchment area, such as the Vukuzazi Study. Clinic and research staff from these activities will notify study nurses of potentially eligible participants who will then conduct eligibility assessments, either at the clinic, or in the case of notification after a home or community-based screening, at participant homes. Study nurses will describe the study and screening procedures, including the required screening for pregnancy and kidney function to confirm eligibility. Those who agree to be screened will have their eligibility determined by the nurse using a screening questionnaire and measurement of blood pressure. Eligible patients who agree to participate will then be asked to review and sign the informed consent form. The study nurse will answer any questions the patients may have about the study. Once informed consent is obtained, the study nurse will conduct the pregnancy test (if applicable) and a point-of-care creatinine test (Abbott/Piccolo Xpress) to complete the enrollment process. Patients who are not pregnant and have glomerular filtration rate greater than 60 ml/min/1.73 m² will be enrolled in the study. Patients who are pregnant, have abnormal renal function, or are confirmed to have uncontrolled hypertension will be referred to clinic for additional care by the nurse and enrollment will not be completed.

E. Informed Consent

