Informed consent procedures will be performed by research nurses who have been trained in the ethical conduct of human subject's research and informed consent procedures. This procedure will be carried out in the participant's in a private area of the home or clinic in either English or in isiZulu. Any eligible patients who previously participated in Aim 1 discussion groups and who are randomly selected for recruitment in the RCT, will be asked to sign the RCT informed consent form if they agree to participate.

F. Randomization

Consenting participants will be randomized by the REDCap randomization module to the standard of care (SOC), (CBPM) or (eCBPM+) study arms (Figure 1). Randomization will be stratified by clinic and active use of anti-hypertensive therapy. Randomization will be conducted in blocks of 9. In brief, after screening has been completed, eligibility confirmed, and informed consent forms signed, a study participant is given a unique consecutive identification number in REDCap. The randomization field is selected, and the research assistant is informed which arm the participant has been selected for by the application. Strategy allocation will be unblinded to participants or clinic staff.

[figure not shown]
G. Aim 2 Study Procedures

a. Blood Pressure Monitoring Procedures by Study Arm

i. SOC: Baseline Visit for Clinic-Based Standard of Care Participants (Figure 2)

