Study recruitment will occur at the Nkundusi and Madwaleni primary health care clinics (PHC) in the AHRI Health and Demographic Surveillance Site (HDSS). All adults who present to these clinics during weekdays will be screened for potential enrolment.

Individuals are eligible to enrol if they:

- Are age ≥ 18 years old
- currently reside in the catchment area of the enrolment clinics with plans to remain in the area for the next 2 years
- have elevated blood pressure (systolic blood pressure >140 mm Hg or diastolic blood pressure >90 mmHg) at screening
- have evidence of at least one previous elevated blood pressure reading in the medical chart 6 months ago or earlier, to meet criteria for hypertension in the South African Department of Health guidelines which require elevated readings on at least two occasions.

Exclusion criteria are

- pregnant women, confirmed by urine β -HCG testing on the day of screening for women aged <55 years, or breastfeeding women
- symptomatic hypertension and a blood pressure >180 mm Hg systolic or 110 mmHg diastolic
- advanced chronic kidney disease (GFR <60 ml/min/1.73m²) as determined by point-of-care creatinine testing
- individuals on three or more anti-hypertensive medications at full dose

4. Randomisation

After informed consent, individuals will be randomised in blocks of 9 to one of the three study arms using the REDCap randomization module. Randomisation will be stratified by the clinic and active use of anti-hypertensive therapy at the time of enrolment.

5. Data collection

At enrolment, participants will be asked about sociodemographic characteristics, medical history and hypertension treatment history, self-reported medication adherence, quality of life, and resource allocation data to enable cost effectiveness analyses.

All participants will be followed up at 6 and 12 months after enrolment, where blood pressure will be measured by study nurses using a standardised Omron BP cuff. Blood pressure will be measured after the participant has been seated for 5 minutes. Three measurements will be taken on the same arm in the seated position, with each measurement taken 5 minutes apart. Data will also be collected on medication regimen changes and adherence, medical history including complications, hospitalizations and treatment side effects, and resource allocation, to enable estimates of program sustainability and longer term costs.

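### A single stated block size of 9, in an open trial with about four strata, makes roughly one allocation in seven fully predictable to anyone tracking a stratum, and no safeguard is described

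*Protocol*

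**What the plan says.** Protocol V.F states: "Randomization will be conducted in blocks of 9". SAP 4 agrees: "individuals will be randomised in blocks of 9 to one of the three study arms using the REDCap randomization module". On strata, Protocol V.F says: "Randomization will be stratified by clinic and active use of anti-hypertensive therapy". SAP 3 fixes the number of clinics at two: "Study recruitment will occur at the Nkundusi and Madwaleni primary health care clinics". Two clinics by two therapy groups gives four strata.

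On blinding, Protocol V.F says: "Strategy allocation will be unblinded to participants or clinic staff". REDCap shows the arm to the research assistant, but only once eligibility is confirmed and consent signed. Under Protocol V.D, clinic and research staff put candidates forward and a study nurse determines eligibility.

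Some exclusion criteria in Protocol V.C need interpretation, among them "Severe, symptomatic hypertension with a measured blood pressure > 180/110 mmHg" and "Planning to move within the next 24 months", as does whether three drugs are each at full dose. The others are measured or tested.

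Neither document mentions varying the block size, keeping it from enrolling staff, or masking study nurses to earlier allocations.

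**The concern.** Central allocation after consent hides the list. It does not hide what can be inferred from past allocations when the block size is known and those allocations are visible. Near the end of each block, someone counting within a stratum can know the next arm before deciding whether to refer, approach or enrol the next person.

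If that knowledge met even limited discretion, the arms could differ in ways the analysis cannot repair. SAP 9.1 adjusts for baseline systolic pressure, clinic and active therapy, which deals largely with selection on blood pressure itself. It does not deal with selection on unmeasured adherence or likelihood of moving away. The latter also bears on missing data, because the primary analysis is complete-case (Protocol V.L, SAP 7).

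**Working it through.** **Inputs.** Block of 9 (Protocol V.F, SAP 4); three equal arms of 258, total 774 (Protocol V.J.a, SAP 6), so 3+3+3 per block; four strata (SAP 3 and 4).

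**The plan's own figure.** The documents give none for predictability. The total of 774 reproduces: 2 × (2.241 + 0.842)² × 19² × (1 − 0.5²) / 5² gives 206 per arm; 206 / 0.80 gives 258; 258 × 3 = 774. That is 774 / 9 = 86 blocks, or about 21.5 per stratum if the strata were equal (an assumption).

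**Certain allocations.** Assume an observer who knows the block size and every earlier allocation in the stratum. In a random ordering of *a* slots of one kind and *b* of another, the expected closing run of the first kind is a / (b + 1).

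| What is certain | Expected slots per block | Share | Of 774 (× 86) |
|---|---|---|---|
| SOC is next | 3 / (6 + 1) = 0.429 | 4.8% | about 37 |
| An intervention is next (SOC used up) | 6 / (3 + 1) = 1.5 | 16.7% | 129 |
| SOC versus intervention, either way | 0.429 + 1.5 = 1.929 | 21.4% | about 166 |
| Exact arm | 3 × 3/7 = 1.286 | 14.3% | about 111 |

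Of the 1.286 slots with a certain exact arm, one is simply the last slot of the block. These shares do not depend on the number of strata while blocks are complete; fewer strata only make counting easier.

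**Best guess.** Exact enumeration over the remaining counts gives 4.787 correct guesses of the exact arm per block (53.2%, against 33.3% by chance). For SOC versus intervention it gives 6.548 (72.8%, against 66.7% from always guessing intervention).

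**Varying blocks.** This was simulated with sizes 6, 9 and 12 equally likely and an observer who knows the possible sizes but not the realised ones. The exact arm is certain for about 2.5% of allocations (runs gave 2.4 to 2.6%, about 19 of 774). SOC versus intervention is certain for about 4% (about 31). The best-guess rate for the exact arm stays near 53%.

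**Possible effect on the estimate (illustration; *d* and *f* are assumptions).** Certain slots make up 0.429 / 3 = 14% of SOC slots and 1.5 / 6 = 25% of intervention slots. Suppose staff shift prognosis by *d* mmHg, beyond baseline pressure, in opposite directions at a fraction *f* of these slots. The bias is then about (0.143 + 0.25) × d × f. With d = 5 it is about 0.5 mmHg at f = 25% and 2.0 mmHg at f = 100%, against the 5 mmHg target difference. With f = 0 it is zero.

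**The case against.** The strongest reply is that the opportunity is narrow and the observer hypothetical.

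- **Discretion is limited.** Age, blood pressure, pregnancy, kidney function and number of drugs are measured or counted. SAP 3 defines raised pressure as either component above threshold plus an earlier chart reading, and plans to screen every adult attending on weekdays. Intention to move rests on what the patient says. This stands: judgement is confined to symptoms, full dose, how stated plans are taken, and the referral or timing of approach.
- **No tally is documented.** The research assistant learns the arm; the study nurse judges eligibility. A reader might infer that enrolling staff know the sequence. The documents do not say so, but they do not exclude shared knowledge, and clinic staff, who may refer candidates, are unblinded.
- **Prediction is modest on average.** A reader might infer that most allocations can be foreseen. About 86% of exact arms are not certain, the best guess is wrong nearly half the time, and for SOC versus intervention it gains only about six percentage points over a constant guess. Deferring a patient because SOC is certainly next could arise at only about 37 allocations.
- **There are some checks.** SAP 8 tabulates reasons for non-eligibility and non-enrolment and summarises baseline characteristics by arm. These could reveal gross manipulation, but not selection on unmeasured factors.
- **Varied blocks leave the average guess rate almost unchanged.** This is true. The gain is in removing certainty.

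**Conclusion.** The point holds as a design weakness of moderate size that is cheap to reduce. The fixed block makes the exact arm certain for 14.3% of allocations and SOC versus intervention certain for 21.4%, for an observer who knows the block size and follows a stratum completely. Those two conditions are assumptions; the documents neither establish nor rule them out.

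The documents do not support the conclusion that selection bias has occurred, that eligibility rests mainly on judgement, or that REDCap fails to conceal the list. The mmHg figures are illustrative only.

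The count of four strata relies on the SAP. Protocol V.J.a refers to three clinics, which would give six strata, and its Table 3 lists eleven. The clinic count should be reconciled, although the percentages do not depend on it.

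**What to change.** In Protocol V.F and SAP 4, for allocations not yet made, replace the fixed block of 9 with 1:1:1 permuted blocks of randomly varying size (for example 6, 9 and 12) within the same strata. Have someone not involved in enrolment generate the sequence and load it as the REDCap allocation table. Keep the sizes out of any document enrolling staff can see.

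The cost is a new allocation table, short text changes and, if enrolment is under way, a protocol amendment. The largest possible difference between two arms from an unfinished block in a stratum rises from 3 to 4, which is small against about 194 per stratum (774 / 4, if equal). The sample size stays at 774.

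The protocol's change summary labels changes from January 2023 as made during or after the trial, and the SAP is dated October 2023, so part or all of the sequence may already be used. For those allocations, report who knew the block size and who could see earlier allocations.
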